## 1 SYNOPSIS

Title: Relative Bioavailability and Effect of Food on DSM265-TPGS 34% SDD Powder in Healthy Adult Subjects	
Background and Rationale:	The current clinical formulation requires reconstitution/administration with a 240 mL sucralose-based vehicle (for a 400 mg adult dose). The new formulation was selected to dissolve in a smaller volume with water (approximately 60 mL for 400 mg adult dose).
Objectives and Endpoints:	The primary objective of this study is to compare the relative bioavailability of the oral DSM265-TPGS 34% SDD powder with the reference DSM265 25% SDD powder for suspension formulation. Another objective of the study is to evaluate the effect of food on the bioavailability of DSM265-TPGS 34% SDD powder.
Investigator(s):	[name]
Study Site(s):	AbbVie Clinical Pharmacology Research Unit (ACPRU)
Study Population and Number of Subjects to be Enrolled:	Approximately 42 healthy adult subjects
Investigational Plan:	This Phase 1, single-dose, open-label study will be conducted according to a randomized parallel group design in adult male and female subjects (3 groups of 14 subjects each). Subjects will be confined for 3 days with outpatient assessments through 21 days. Blood samples will be collected for 480 hours after dosing.
Key Eligibility Criteria:	Volunteers in general good health. Women must be of non-child bearing potential (WONCBP).
Study Drug and Duration of Treatment:	Single dose of 400 mg DSM265 25% SDD (Reference) Single dose of 400 mg DSM265 TPGS 34% SDD (Test)
Date of Protocol Synopsis:	13 August 2018

## 2 INTRODUCTION

### 2.1 Background and Rationale

---

#### Why Is This Study Being Conducted

DSM265 is a new antimalarial drug candidate targeted for acute uncomplicated malaria (single dose cure) and possibly chemoprevention (repeated administration) being developed by Medicines for Malaria Venture (MMV). This new chemical entity is being evaluated in various Phase 1 studies and has been also tested in a Phase 2A trial in patients with acute uncomplicated malaria. The highest dose tested in the first-in-human study was 1200 mg and it has been shown to be well tolerated. Clinical data from a human malaria challenge model in healthy subjects as well as efficacy results from the Phase 2A trial suggests that efficacy in acute uncomplicated malaria with Plasmodium falciparum can be achieved with a single 400 mg dose of DSM265.

The median time to the maximum observed plasma concentration ( $C_{max}$ ), time to  $C_{max}$  ( $T_{max}$ ), was approximately 4 hours at a dose of 400 mg and the mean terminal phase elimination half-life ( $t_{1/2}$ ) remained constant across doses, ranging from 85 to 112 hours. A major metabolite, DSM450, was identified with  $T_{max}$  of 96 to 144 hours after dosing, a mean  $t_{1/2}$  ranging from 131 to 168 hours, and an area under the plasma concentration-time curve (AUC) of approximately 0.19 to 0.28 relative to that of DSM265.

This Phase 1 study is designed to evaluate the relative bioavailability of a single dose of a test formulation, DSM265-TPGS 34% SDD powder, with the reference DSM265 25% SDD powder for suspension formulation used in previous clinical trials. This Phase 1 study is also designed to evaluate the effect of food on the bioavailability of DSM265-TPGS 34% SDD powder.

### 2.2 Benefits and Risks to Subjects

---

There are no expected direct benefits for subjects who enroll in this healthy volunteer study. Study drugs may be associated with adverse effects as detailed in the subject informed consent form(s). Not all of the potential side effects of the study drugs may be known. In addition, subjects may experience discomfort or inconvenience related to study procedures.

For further details, reference findings from completed studies, including safety data in the DSM265 Investigator's Brochure.

## 3 STUDY OBJECTIVES AND ENDPOINTS

### 3.1 Objectives

---

The primary objective of this study is to compare the relative bioavailability of the oral DSM265-TPGS 34% SDD powder to the reference DSM265 25% SDD powder for suspension formulation. Another

objective of the study is to evaluate the effect of food on the bioavailability of DSM265-TPGS 34% SDD powder.

## 3.2 Safety Endpoints

---

Safety evaluations will include adverse event (AE) monitoring, physical examinations, vital signs measurements, electrocardiogram (ECG) variables and clinical laboratory testing.

## 3.3 Pharmacokinetic Endpoints

---

The values for the pharmacokinetic parameters of DSM265 and possible metabolite(s) including  $C_{max}$ ,  $T_{max}$ , apparent terminal phase elimination rate constant ( $\beta$ ),  $t_{1/2}$ , AUC from time 0 until the last measurable concentration ( $AUC_t$ ), AUC from time 0 to 168 hours ( $AUC_{168}$ ) and AUC from time 0 to infinity ( $AUC_{inf}$ ) will be determined using non-compartmental methods. Plasma concentration at 168 hours ( $C_{168}$ ) will also be measured. Additional parameters may be estimated if useful in the interpretation of the data. In addition, the blood samples may be used for other exploratory analysis.

# 4 INVESTIGATIONAL PLAN

[figure not shown]
## 4.1 Overall Study Design and Plan

---

The schematic of the study is shown in [Figure 1](#). Further details regarding study procedures are located in the Operations Manual ([Appendix E](#)).

See Section [5.1](#) for information regarding eligibility criteria.

**Figure 1. Single-Dose, Open-Label, Randomized Parallel Group Design in Healthy Volunteers**

## 4.2 Discussion of Study Design

### Discussion of Study Design and Choice of Control Groups

Each subject will be randomly assigned to one of the regimens to avoid bias. Parallel groups will be utilized as the half-life of DSM265 ranges from 85 to 112 hours.

### Appropriateness of Measurements

Standard pharmacokinetic, statistical, clinical, and laboratory procedures will be utilized in this study.

### Suitability of Subject Population

The selection of subjects in general good health is standard for pharmacokinetic studies.

### Selection of Doses in the Study

The dose of 400 mg was tested in the Phase 2A proof-of-concept clinical study and demonstrated the potential to be an efficacious dose for the treatment of uncomplicated malaria with *Plasmodium falciparum* with an acceptable safety profile.

### Blinding

This is an open-label study.

## Meals and Dietary Requirements

At least a ten-hour fast is required prior to dosing for Regimen A and Regimen B, a high-fat breakfast is required for Regimen C; otherwise, standard moderate-fat meals will be provided during confinement.

## 5 STUDY ACTIVITIES

### 5.1 Eligibility Criteria

---

Subjects must meet all of the following criteria in order to be included in the study. Anything other than a positive response to the questions below will result in exclusion from study participation. A subject who has failed screening may be re-screened at investigator's discretion.

#### Consent

- ✓ 1. Subjects or their legally authorized representative must voluntarily sign and date each informed consent, approved by an Independent Ethics Committee (IEC)/Institutional Review Board (IRB), prior to the initiation of any screening or study-specific procedures.

#### Demographic

- ✓ 2. Male or female between 18 and 55 years of age inclusive at the time of screening.
- ✓ 3. Body Mass Index (BMI) is  $\geq 18.0$  to  $\leq 29.9$  kg/m^2 after rounding to the tenths decimal. BMI is calculated as weight in kg divided by the square of height measured in meters.

#### Contraception Eligibility and Guidance

- ✓ 4. Females must be of Non-Childbearing Potential as defined below:  
Females do not need to use birth control during or following study drug treatment if considered of non-childbearing potential due to meeting any of the following criteria:
  - Postmenopausal, age  $\leq 55$  years with no menses for 12 or more months without an alternative medical cause AND an follicle stimulating hormone (FSH) level  $> 40$  IU/L.
  - Permanently surgically sterile (bilateral oophorectomy, bilateral salpingectomy, or hysterectomy).
- ✓ 5. Female who is not pregnant, breastfeeding, or considering becoming pregnant during the study or for approximately 120 days after the last dose of study drug.
- ✓ 6. Male subjects who are sexually active with a female partner of childbearing potential, must agree to use condoms, even if the male subject has undergone a successful vasectomy, from Study Day 1 through 120 days after the last dose of study drug. His female partner(s) must also use at least one of the following methods of birth control:
  - Combined (estrogen and progestogen containing) hormonal birth control (oral, intravaginal, injectable, transdermal) associated with inhibition of ovulation initiated at least 30 days prior to study Baseline Day 1.

- Progestogen-only hormonal birth control (oral, injectable, implantable) associated with inhibition of ovulation initiated at least 30 days prior to study Baseline Day 1.
- bilateral tubal occlusion/ligation
- intrauterine device (IUD)
- Intrauterine hormone-releasing system (IUS)
- ✓ 7. Male who is not considering fathering a child or donating sperm during the study or for approximately 120 days after the last dose of study drug.

## Laboratory Assessments and ECG Criteria

- ✓ 8. Laboratory values meet the following criteria:
  - serum aspartate transaminase (AST) and alanine transaminase (ALT)  $\leq$  the upper limit of normal (ULN) at the Screening Visit and upon initial confinement.
  - negative test result for hepatitis A virus immunoglobulin M (HAV-IgM), hepatitis B surface antigen (HBsAg), hepatitis C virus (HCV) antibody (Ab) and human immunodeficiency virus (HIV) at screening visit.
  - negative screen for drugs of abuse, alcohol or cotinine at screening and upon initial confinement.
  - for non-postmenopausal female subjects, a negative urine pregnancy test at the screening visit and a negative serum pregnancy test upon initial confinement and prior to the first dose of study drug.
  - no other laboratory results that the investigator determines are clinically significant.
  - platelets greater than or equal to the lower limit of normal.
- ✓ 9. No clinically significant ECG abnormalities including
  - no evidence of 2nd or 3rd degree AV block at screening visit and upon initial confinement.
  - QT interval corrected for heart rate (QTc) using Fridericia's correction formula (QTcF) is  $\leq$  430 msec (males) or  $\leq$  450 msec (females) at screening visit and upon initial confinement.

## Subject History/Physical Exam and Vital Signs

- ✓ 10. A condition of general good health, based upon the results of a medical history, physical examination, vital signs, laboratory profile and a 12-lead ECG.
- ✓ 11. No history of: epilepsy, any clinically significant cardiac, respiratory (except mild asthma as a child), renal, hepatic, gastrointestinal, hematologic or psychiatric disease or disorder, or any uncontrolled medical illness.
- ✓ 12. No history of any clinically significant sensitivity or allergy to any medication or food.
- ✓ 13. No history of or active medical condition(s) or surgical procedure(s) that might affect gastrointestinal motility, pH, or absorption [e.g., Crohn's disease, celiac disease, gastroparesis, short bowel syndrome, gastric surgery (except pyloromyotomy for pyloric stenosis during infancy), cholecystectomy, vagotomy, bowel resection].

- ✓ 14. No evidence of dysplasia or history of malignancy (including lymphoma and leukemia) other than successfully treated non-metastatic cutaneous squamous cell, basal cell carcinoma or localized carcinoma in situ of the cervix.
- ✓ 15. No history of any clinically significant illness/infection/major febrile illness, hospitalization, or any surgical procedure within 30 days prior to the first dose of study drug.
- ✓ 16. Has not donated blood (including plasmapheresis), lost  $\geq$  550 mL blood volume, or received a transfusion of any blood product within 8 weeks prior to study drug administration.
- ✓ 17. No consumption of alcohol, grapefruit products, Seville oranges, starfruit products or quinine/tonic water within the 72-hour period prior to study drug administration.
- ✓ 18. No use of tobacco or nicotine-containing products within 180 days prior to the first dose of study drug.
- ✓ 19. No history of clinically significant (per Investigator's judgment) drug or alcohol abuse within the last 6 months.
- ✓ 20. Is not currently enrolled in another interventional clinical study.
- ✓ 21. Has not been previously enrolled in this study.
- ✓ 22. In the opinion of the investigator, this subject is a suitable candidate for enrollment in the study.

### Concomitant Medications

- ✓ 23. Subjects must not have been treated with any investigational drug within 30 days or 5 half-lives of the drug (whichever is longer) prior to the first dose of study drug.
- ✓ 24. Subject must not have received any live vaccine within 4 weeks prior to the first dose of study drug, or expected need of live vaccination during study participation including at least 4 weeks after the last dose of study drug.
- ✓ 25. Subject must not require any over-the-counter and/or prescription medication, vitamins and/or herbal supplements, with the exception of contraceptives or hormonal replacement therapies for females, on a regular basis.
- ✓ 26. Subject must not use any medications within the 2-week period prior to study drug administration.
- ✓ 27. Receipt of any drug by injection within 30 days or within a period defined by 5 half-lives, whichever is longer, prior to study drug administration.
- ✓ 28. No use of known inhibitors (e.g., ketoconazole) or inducers (e.g., carbamazepine) of cytochrome P450 3A (CYP3A) within 1 month prior to study drug administration.
- ✓ 29. No exposure to DSM265 within the past 90 days prior to first dose of study drug.

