## 5.2 Prior and Concomitant Therapy

---

Any medication or vaccine (including over-the-counter or prescription medications) that the subject receives after enrollment into the study must be recorded through the last study visit.

---

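### Criterion 27 has lost its negation, so read literally it requires a recent injection; a lesser point is that criterion 26 does not repeat the hormone-therapy exception in criterion 25

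*Protocol*

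**What the plan says.** Protocol section 5.1 sets the reading rule for the whole list: "Subjects must meet all of the following criteria in order to be included in the study", and "Anything other than a positive response to the questions below will result in exclusion from study participation". There is no separate exclusion list, so prohibitions have to be written as negated statements. Criterion 18 shows the usual form: "No use of tobacco or nicotine-containing products within 180 days prior to the first dose of study drug".

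Under the Concomitant Medications heading of the same section:

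- Criterion 23: "Subjects must not have been treated with any investigational drug within 30 days or 5 half-lives of the drug (whichever is longer"), counted back from the first dose.
- Criterion 25 bars medication needed regularly, "with the exception of contraceptives or hormonal replacement therapies for females, on a regular basis".
- Criterion 26: "Subject must not use any medications within the 2-week period prior to study drug administration". It states no exception.
- Criterion 27: "Receipt of any drug by injection within 30 days or within a period defined by 5 half-lives, whichever is longer", counted back from study drug administration. It contains no negative word.

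**The concern.** There are two separate points, of unequal strength.

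The main one is criterion 27. Combined with the reading rule at the head of section 5.1, its wording reverses what it is evidently meant to do. A volunteer with no recent injection cannot answer it positively and is excluded, while a volunteer with one satisfies it. This is an enrolment rule, not background text. Section 5.7 prohibits protocol deviations except to remove an immediate hazard and requires any that occur to be notified. Read strictly, enrolling an ordinary healthy volunteer would breach the written criterion, and site staff should not have to reverse a criterion by inference.

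The secondary point is whether the exception for female hormonal products in criterion 25 is meant to survive criterion 26. The text does not show whether the narrowing was intended.

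**Working it through.** There is no stated figure to reproduce. The check is a count of wording and a side-by-side reading.

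**Criterion 27: count of negations**

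1. Medication items are criteria 23 to 29: 29 − 23 + 1 = 7. Negated: 23, 24, 25, 26, 28 and 29, which is 6. Not negated: 27, so 7 − 6 = 1.
2. Items with a *within a stated period* window on the subject's own history, taken from the history and medication parts of section 5.1:

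| Criterion | Window | Negated |
|---|---|---|
| 15 | 30 days | yes |
| 16 | 8 weeks | yes |
| 17 | 72 hours | yes |
| 18 | 180 days | yes |
| 19 | 6 months | yes |
| 23 | 30 days or 5 half-lives | yes |
| 24 | 4 weeks | yes |
| 26 | 2 weeks | yes |
| 27 | 30 days or 5 half-lives | **no** |
| 28 | 1 month | yes |
| 29 | 90 days | yes |

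That gives 11 items, 10 negated, and 11 − 10 = 1 not negated: criterion 27.

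3. The count of 11 depends on the definition of a look-back item. It leaves out criterion 21 (previous enrolment, no window), the 12 months without menses in criterion 4 (a definition) and the 30-day start of partner contraception in criterion 6 (a requirement, not a washout). Another definition could change the 11, but criterion 27 would still be the only prohibition-type item without its negation.
4. Criterion 23 has the same window, the longer of 30 days and 5 half-lives, and is worded as a prohibition. That makes the intent of 27 evident.

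**Criteria 25 and 26: one case followed through**

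Take a woman on regular hormone replacement who is otherwise eligible.

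- Criterion 25: her therapy is excepted, so she passes.
- Criterion 26: she has used a medication within 2 × 7 = 14 days of dosing and no exception is stated, so she fails.
- Section 5.1 requires all criteria to be met, so she is excluded.

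The exception in 25 therefore helps only where the product was last used more than 14 days before dosing, which sits oddly with an exception for regular use. Nothing elsewhere restores it. Section 5.2 says only that medication "that the subject receives after enrollment into the study must be recorded through the last study visit", and Operations Manual section 3.2 likewise asks only for recording, from 2 weeks before dosing. If criterion 27 is corrected to a prohibition without further change, it too will carry no exception for injected hormonal products.

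**The case against.** On criterion 27, the fair reply is that it is a noun fragment, not a sentence demanding an injection. The requirement appears only when it is joined mechanically to the reading rule. It stands among washout items and directly follows a bar on all medication, and site staff would see at once that the literal reading excludes nearly everyone. That limits the practical consequence and holds the point at minor. It does not remove the error: nothing elsewhere in the protocol supplies the missing word, and the item is a numbered entry with no sign of redaction or a broken table. The counts show that the wording is out of line; they do not measure impact.

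On criteria 25 and 26, a reader might infer a contradiction. The documents do not support that. One item asks about medication needed regularly, the other about use in the 2 weeks before dosing. Both can be applied, the stricter governs, and the pair admits no one wrongly. A missing counterpart exception is not in itself an error. What stands is a question of clarity, because the exception has been largely emptied.

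Nor can the size of the second point be shown. Criterion 4 admits only women of non-childbearing potential, so it concerns mainly hormone replacement, in a study of about 42 subjects. The protocol gives no number of women who might be affected.

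**Conclusion.** The point holds for criterion 27: it is wrong as written. It is the single item without a negation out of 7 medication items and out of 11 look-back items, and under section 5.1's own rule it requires what it is evidently meant to bar. That the intent is a prohibition is an inference from the neighbouring items and from the shared window in criterion 23; the protocol does not say so directly.

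For criteria 25 and 26 the conclusion is narrower. They are compatible, but criterion 26 leaves the exception in 25 with almost no effect, and the intent is unclear.

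Severity is minor. A reader might infer that the pharmacokinetic comparison is compromised; the documents give no ground for that, since no endpoint, sample size or analysis rests on these items.

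**What to change.** Correct the polarity of criterion 27 so that it matches its neighbours.

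Reconcile criteria 25, 26 and the corrected 27 by stating whether the exception for female hormonal products carries over to 26 and 27, including for injected products. Which rule applies is for the sponsor to decide.

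The cost is a few words in criteria 25 to 27 of section 5.1, and in any site eligibility form that repeats them. Section 8.1 requires ethics committee approval of any protocol amendment before it is implemented, so the change would go through that route. Design, sample size and analysis stay as they are.

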## 5.2 Prior and Concomitant Therapy

---

Any medication or vaccine (including over-the-counter or prescription medications) that the subject receives after enrollment into the study must be recorded through the last study visit.

---

## 5.3 Withdrawal of Subjects and Discontinuation of Study

---

A subject may voluntarily withdraw or be withdrawn from the study at any time for reasons including, but not limited to, the following:

- The Investigator believes it is in the best interest of the subject.
- The subject requests withdrawal from the study.
- The subject becomes pregnant while on study drug.
- Subject is significantly noncompliant with study procedures, which would put the subject at risk for continued participation in the trial.

AbbVie or MMV may terminate this study prematurely, either in its entirety or at any site. The Investigator may also stop the study at his/her site if he/she has safety concerns. If AbbVie or MMV terminates the study for safety reasons, AbbVie will promptly notify the Investigator.

## 5.4 Follow-Up for Subject Withdrawal from Study

---

In the event that a subject withdraws or is discontinued from the study, the primary reason for discontinuation and any other reason(s) for the discontinuation from the study will be recorded and a physical examination, body weight, vital signs measurement, ECG, laboratory analyses, and an assessment of adverse events will be performed as soon as possible after discontinuation from the study. Additional blood samples for drug measurement may be collected at the time of discontinuation from subjects who are discontinued due to adverse events; the clock time, time in relation to dose, and date the sample was taken will be recorded.

If a subject is discontinued from the study with an ongoing adverse event or an unresolved laboratory result that is significantly outside of the reference range, the investigator will attempt to provide follow-up until a satisfactory clinical resolution of the laboratory result or adverse event is achieved.

## 5.5 Study Drug

---

Information about the DSM265 formulations to be used in this study is presented in [Table 1](#).

**Table 1. Identity of Investigational Products**

	DSM265 Regimens	
	Reference	Test
Dosage Form	Powder for suspension	Powder for suspension
Formulation	25% SDD	TPGS 34% SDD
Strength (mg)	400	400
Drug Preparation	Reconstitute in 100 mL supplied vehicle; rinse twice with 70 mL supplied vehicle	Reconstitute in 40 mL water + 20 mL rinse water
Additional Information	Store at 2 to 8°C/35 to 46°F	Store at 2 to 8°C/35 to 46°F

